12.2.5. Analysis of Safety Variables

Adverse events will be mapped to the Medical Dictionary for Regulatory Activities (MedDRA) preferred term and system organ classification. The occurrence of TEAEs will be summarized using MedDRA preferred terms, system organ classifications, and severity (eg, Grade 3 or 4) by cohort and for all subjects. Separate summaries of treatment-emergent SAEs and AEs related to study drug will be generated, as well as AEs leading to study drug being interrupted or study withdrawal. All AEs will be listed for individual subjects showing both verbatim and preferred

terms. Adverse events that are reported during the SOC treatment period will be summarized separately.

Descriptive summaries of clinical laboratory results will be presented by study visit by cohort. Laboratory abnormalities will be graded according to the DAIDS Table for Grading Adverse Events for Adults and Pediatrics (Corrected Version 2.1, July 2017) unless otherwise specified. In addition to DAIDS requirements, creatinine increases from baseline must also meet certain minimum thresholds, to appropriately target meaningful changes in creatinine in pediatric patients with low baseline values, as summarized below:

- Grade 1 mild: 1.1 to 1.3 x ULN OR increase ≥ 0.2 mg/dL from participant's baseline
- Grade 2 moderate: > 1.3 to 1.8 x ULN OR increase ≥ 1.3 x baseline AND increase ≥ 0.3 mg/dL from baseline
- Grade 3 severe: > 1.8 to 3.5 x ULN OR increase ≥ 1.5 x baseline AND increase ≥ 0.5 mg/dL from baseline)
- Grade 4 potentially life threatening: > 3.5 x ULN OR Increase ≥ 2 x baseline AND increase ≥ 0.7 mg/dL from baseline

The number and percentage of subjects experiencing treatment-emergent graded toxicities will be summarized. Laboratory toxicity shifts from baseline to post-baseline assessments will be summarized or listed by cohort.

Effects of berotralstat on pediatric patient growth (weight, height, and BMI) will be assessed over time by cohort. Vital signs, laboratory data (eg, chemistry, hematology, and urinalysis results), and ECGs will also be summarized over time by cohort.

Previous and concomitant medications will be mapped to a World Health Organization preferred term and drug classification. The number and percentage of subjects taking concomitant medications will be summarized using preferred terms and drug classifications (including during the SOC treatment period).

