PARAMETER	GRADE 1 MILD	GRADE 2 MODERATE	GRADE 3 SEVERE	GRADE 4 POTENTIALLY LIFE- THREATENING
Arrhythmia (by ECG or physical examination) Specify type, if applicable	No symptoms AND No intervention indicated	No symptoms AND Non-urgent intervention indicated	Non-life-threatening symptoms AND Non-urgent intervention indicated	Life-threatening arrhythmia OR Urgent intervention indicated
Blood Pressure Abnormalities¹ Hypertension (with the lowest reading taken after repeat testing during a visit) ≥ 18 years of age	140 to < 160 mmHg systolic OR 90 to < 100 mmHg diastolic	≥ 160 to < 180 mmHg systolic OR ≥ 100 to < 110 mmHg diastolic	≥ 180 mmHg systolic OR ≥ 110 mmHg diastolic	Life-threatening consequences in a participant not previously diagnosed with hypertension (e.g., malignant hypertension) OR Hospitalization indicated
< 18 years of age	> 120/80 mmHg	≥ 95 th to < 99 th percentile + 5 mmHg adjusted for age, height, and gender (systolic and/or diastolic)	≥ 99 th percentile + 5 mmHg adjusted for age, height, and gender (systolic and/or diastolic)	Life-threatening consequences in a participant not previously diagnosed with hypertension (e.g., malignant hypertension) OR Hospitalization indicated
Hypotension	No symptoms	Symptoms corrected with oral fluid replacement	Symptoms AND IV fluids indicated	Shock requiring use of vasopressors or mechanical assistance to maintain blood pressure
Cardiac Ischemia or Infarction Report only one	NA	NA	New symptoms with ischemia (stable angina) OR New testing consistent with ischemia	Unstable angina OR Acute myocardial infarction
Heart Failure	No symptoms AND Laboratory or cardiac imaging abnormalities	Symptoms with mild to moderate activity or exertion	Symptoms at rest or with minimal activity or exertion (e.g., hypoxemia) OR Intervention indicated (e.g., oxygen)	Life-threatening consequences OR Urgent intervention indicated (e.g., vasoactive medications, ventricular assist device, heart transplant)

¹ Blood pressure norms for children < 18 years of age can be found in: Expert Panel on Integrated Guidelines for Cardiovascular Health and Risk Reduction in Children and Adolescents. *Pediatrics* 2011;128;S213; originally published online November 14, 2011; DOI: 10.1542/peds.2009-2107C.

Cardiovascular

PARAMETER	GRADE 1 MILD	GRADE 2 MODERATE	GRADE 3 SEVERE	GRADE 4 POTENTIALLY LIFE- THREATENING

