6.8.1. Multiple Assessments

Where multiple scheduled measurements are recorded for a given time point (ie, triplicate ECGs or repeated blood pressure assessments), the mean of the measurements will be calculated and used in any derivation of summary statistics. All available data will be listed.

When multiple visits occur within the same window, the scheduled visit will be used in the analysis if available. If no scheduled visit occurs within the window and unscheduled visit(s) and/or an early termination visit occur within the window, the analysis visit closest to the target day will be selected for use in analysis. If deemed appropriate by the sponsor (eg, in the case of a

retest), unscheduled visits may be chosen for analysis given documentation of the desired visit from the sponsor.

Results from unscheduled visits will be eligible for inclusion in analyses of worst post-baseline results regardless of their use for 'by visit' displays.

Listings will display all visits as recorded on the eCRF, including the date and study day. All available data including any totals, domains, or subscales of scale assessments summarized will be listed.

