11.6. Vital Signs

Descriptive summaries of vital signs (blood pressure, temperature, pulse, respiratory rate, height, weight, BMI) and change from baseline vital signs will be presented by parameter, time point, and cohort. Vital signs and physical examination results will each be listed by cohort, subject, and time point.

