X	X	X	14.3.1.13.4	Subjects Reporting Treatment-emergent Adverse Events in the Hypersensitivity, Anaphylactic Reaction or Severe Cutaneous Reaction SMQs	Safety
X	X	X	14.3.1.14	Subjects Reporting Treatment-emergent Adverse Events in the Torsade de pointes/QTc Prolongation SMQ or Palpitation Preferred Term	Safety
X	X	X	14.3.1.15	Overall Summary of Adverse Events During the SOC Treatment Period	Safety
X	X	X	14.3.1.16	Subjects Reporting Adverse Events During the SOC Treatment Period by MedDRA System Organ Class and Preferred Term	Safety
X	X	X	14.3.4.1.1	Summary of Observed and Change from Baseline in Clinical Chemistry Laboratory Parameters	Safety
X	X	X	14.3.4.1.2	Summary of Observed and Change from Baseline in Hematology and Coagulation Laboratory Parameters	Safety
X	X	X	14.3.4.1.3	Summary of Observed and Change from Baseline in Quantitative Urinalysis Laboratory Parameters	Safety
X	X	X	14.3.4.2.1	Summary of Elevations in Post-Baseline Liver Function Tests	Safety
X	X	X	14.3.4.2.2	Hy's Law Plot of Maximum Total Bilirubin vs. Maximum ALT	Safety

NDA IA	End of Part 2 (Wk 48) IA†	Final/ EOS**	Output Number	Title	Population
X	X	X	14.3.4.2.3	Liver Test Safety Panel Over Time, Baseline vs. On-Study	Safety
X	X	X	14.3.4.2.4	Distribution of Liver Tests Over Time: ALT, AST, ALP, and Bilirubin	Safety
X	X	X	14.3.4.3	Treatment-Emergent Grade 3 and 4 Laboratory Toxicities by DAIDS Grades*	Safety
X	X	X	14.3.4.4.1	Shift from Baseline to Worst Post-baseline Assessment: Clinical Chemistry	Safety
X	X	X	14.3.4.4.2	Shift from Baseline to Worst Post-baseline Assessment: Hematology and Coagulation	Safety
X	X	X	14.3.4.4.3	Shift from Baseline to Worst Post-baseline Assessment: Urinalysis	Safety
X	X	X	14.3.5.1.1	Observed and Change from Baseline in 12-Lead ECG	Safety
X	X	X	14.3.5.1.2	12-Lead ECG Interpretation	Safety
X	X	X	14.3.5.1.3	12-Lead ECG QTcF Interval Categories	Safety
X	X	X	14.3.5.2.1	Observed and Change from Baseline in Vital Signs	Safety
X	X	X	14.3.5.3.1.1	Plot of Mean (SD) QTcF Observed Changes Relative to Baseline Over Time	Safety
X	X	X	14.3.5.3.1.2	Distribution Plots for QTcF Observed Changes Relative to Baseline Over Time	Safety
X	X	X	14.3.5.3.1.3	Distribution Plots for QTcF Observed Changes Relative to Baseline – All Observations	Safety
X	X	X	14.3.5.3.2.1	Plot of Mean (SD) PR Interval Observed Changes Relative to Baseline Over Time	Safety
X	X	X	14.3.5.3.2.2	Distribution Plots for PR Interval Observed Changes Relative to Baseline Over Time	Safety

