X	X	X	16.2.7.2.5	Grade 3 or 4 Treatment-emergent Adverse Events	Safety
X	X	X	16.2.7.2.6.1	Subjects Reporting Treatment-emergent Adverse Events in the Hypersensitivity SMQ	Safety
X	X	X	16.2.7.2.6.2	Subjects Reporting Treatment-emergent Adverse Events in the Anaphylactic Reaction SMQs	Safety
X	X	X	16.2.7.2.6.3	Subjects Reporting Treatment-emergent Adverse Events in the Severe Cutaneous Adverse Reaction SMQ	Safety
X	X	X	16.2.7.2.7	Subjects Reporting Treatment-emergent Adverse Events in the Torsade de pointes/QT Prolongation SMQ or Palpitation Preferred Term	Safety
X	X	X	16.2.7.2.8	Treatment-emergent Adverse Events Leading to Interruption of Study Drug	Safety
X	X	X	16.2.7.2.9	Treatment-emergent Adverse Events Leading to Discontinuation of Study Drug	Safety
X	X	X	16.2.7.2.10	Fatal Serious Treatment-emergent Adverse Events	Safety
X	X	X	16.2.8.1.1	Laboratory Results - Clinical Chemistry	Safety
X	X	X	16.2.8.1.2	Laboratory Results – Hematology	Safety
X	X	X	16.2.8.1.3	Laboratory Results - Coagulation	Safety
X	X	X	16.2.8.1.4	Laboratory Results - Urinalysis	Safety
X	X	X	16.2.8.1.5	Grade 3 or 4 Laboratory Results	Safety
X			16.2.8.1.6	Laboratory Results – C1-INH Level, C1-INH Function and Screening C4	Safety
X			16.2.8.2	Laboratory Results - SERPING-	Safety
X	X	X	16.2.8.3	Pregnancy Tests	Safety
X	X	X	16.2.8.4	12-Lead Electrocardiogram	Safety
X	X	X	16.2.8.5	Vital Signs, Height, Weight, and BMI	Safety
X	X	X	16.2.8.6	Physical Examinations	Safety
X			16.2.9.1	Acceptability/Palatability of the Berotralstat Oral Granules	Safety

Abbreviations: ALP = alkaline phosphatase; ALT = alanine transaminase; AST = aspartate transaminase; BMI = body mass index; C1-INH = C1-esterase inhibitor; C4 = complement 4; CONSORT = consolidated standards of reporting trials; DAIDS = Division of AIDS; ECG = electrocardiogram; EOS = end of study; HAE = hereditary angioedema; IA = interim analysis; ITT = intent to treat; MedDRA = Medical Dictionary for Regulatory Activities; NDA = New Drug application; PK = pharmacokinetics; QTcf = corrected QT interval using Fridericia's formula; SD = standard deviation; SMQ = standardized MedDRA query; SOC = standard of care; Wk = week.

*Except as noted in the protocol or SAP

**These tables will also likely be included in any Safety data update required by regulatory agencies.

†Safety and dosing tables for the end of 48-week analysis will only include data through Week 48; for all other analyses, all available data will be reported unless otherwise specified.

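### No planned table compares measured blood pressure with the paediatric limits in the protocol's own grading table; only raw mmHg and raw change are summarised

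*Protocol*

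**What the plan says.** Vital signs are part of the secondary safety endpoint (Protocol Section 5.2.2, SAP Section 3.2.2).

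- **Protocol Section 12.2.5:** "Vital signs, laboratory data (eg, chemistry, hematology, and urinalysis results), and ECGs will also be summarized over time by cohort". It names no threshold, category or grade for blood pressure.
- **SAP Section 11.6:** "Descriptive summaries of vital signs (blood pressure, temperature, pulse, respiratory rate, height, weight, BMI) and change from baseline vital signs will be presented". The breakdown is per measure and visit within each cohort.
- **SAP Section 14.1:** the display list has one vital-signs table, 14.3.5.2.1, titled "Observed and Change from Baseline in Vital Signs", and one listing, 16.2.8.5, titled "Vital Signs, Height, Weight, and BMI".
- **Protocol Section 15.1 (DAIDS table, cardiovascular part):** for children under 18 years, Grade 1 hypertension is a fixed limit of more than 120/80 mmHg. Grade 2 runs from the 95th percentile up to a limit set at the 99th "percentile + 5 mmHg adjusted for age, height, and gender (systolic and/or diastolic"), and Grade 3 starts at that limit. Grade 4 is defined clinically. A footnote cites the paediatric norms.
- **Repeat readings:** the DAIDS row is headed "Hypertension (with the lowest reading taken after repeat testing during a visit"), while SAP Section 6.8.1, for summary statistics, says of "repeated blood pressure assessments), the mean of the measurements will be calculated".

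Laboratory values are DAIDS-graded by program and have shift tables to the worst post-baseline grade (SAP Sections 6.7.6 and 11.3.1). QTcF has outlier categories by number and percentage of subjects (SAP Section 11.5).

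**The concern.** The children enter at 2 to under 12 years and may be treated for up to 144 weeks. Over that time their age and height change, and so do the percentile limits that apply to them. A raw change in mmHg does not separate growth from a drug effect, and there is no concurrent control group to separate them by comparison.

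The protocol appends a standard that makes the needed adjustment for Grades 2 and 3, but the analysis plan does not apply it to the measured pressures. The number of children whose measured pressure moved across a paediatric limit on berotralstat is therefore not a planned result. It would be known only for children whose investigator recognised the reading as abnormal for that child and reported an adverse event.

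**Working it through.** **1. The plan's own figure.** Protocol Section 12.1 gives about a 96% chance of seeing at least one treatment-emergent adverse event of 10% frequency in 30 subjects. Check: 1 − 0.9^30 = 0.9576, which agrees. The figure concerns events that become adverse events. It says nothing about measured values that do not.

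**2. Planned displays side by side.**

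| Measure | Observed and change | Graded or categorised | Shift to worst value |
|---|---|---|---|
| Laboratory values | yes | yes, DAIDS | yes |
| QTcF | yes | yes, fixed ranges | none listed |
| Blood pressure | yes | no | no |

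SAP Section 8.6 (values of clinical concern) names QTcF only. SAP Section 6.8 keeps unscheduled and early-termination data for worst post-baseline assessments, but no such display exists for blood pressure.

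**3. What the raw table can show.** Treatment of 144 weeks is 144 × 7 / 365.25 = 2.76 years. As an illustration, assume that one child rises 25 mmHg, the others do not change, and the SD of change is 10 mmHg. None of these values is in the documents.

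- Cohort of 4 (the minimum for Cohorts 1 to 3): mean shift 25/4 = 6.25 mmHg, SEM 10/√4 = 5.0.
- Cohort of 8 (assumed; 30/4 = 7.5 children per cohort if evenly spread): mean shift 25/8 = 3.1 mmHg, SEM 10/√8 = 3.5.

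The mean alone is hard to tell from noise. The maximum change would print as +25, because SAP Section 6.4 requires minimum and maximum. It would not show whether that child is above the 95th percentile for age, sex and height. The largest raw pressure in a cohort need not belong to the child furthest above his or her own limit.

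**4. What the adverse-event route can show.** Adverse events are DAIDS-graded (Protocol Section 11.1.1.4, SAP Section 11.1) and tabulated by preferred term, severity and cohort (Tables 14.3.1.2, 14.3.1.3 and 14.3.1.7). Under Protocol Section 11.1.1.1, a diagnostic finding that leads to no treatment, extra visit or further monitoring is not an adverse event. Applied to blood pressure, a high reading that nobody acts on appears only as a raw value.

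**5. Whether the data allow a better summary.** Month and year of birth and sex are collected (Protocol Section 10.1). Blood pressure is measured at every clinic visit in the schedule of assessments. Height is recorded at screening, Day 1, Weeks 12, 24, 36, 48, 72, 96, 120 and 144, and the end-of-study visit. It is not scheduled at Weeks 2 and 6, so the most recent height must be used there.

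**6. Chance flags in a worst-value count.** The scheduled post-baseline blood pressure visits are Weeks 2, 6, 12, 24, 36, 48, 72, 96, 120 and 144 plus end of study, which makes 11. Assume children who resemble the reference population and no drug effect. The chance that at least one of 11 readings of one pressure is at or above the 95th percentile is:

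- perfectly correlated visits: 0.05, or 5%;
- independent visits: 1 − 0.95^11 = 0.431, or 43%.

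The truth lies between these, at a point the documents do not determine. Counting systolic and diastolic together could raise it.

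**The case against.** The strongest reply is that the plan breaks no commitment. The documents use DAIDS for adverse-event severity and for laboratory values, and they never promise to grade vital signs by program. The extra attention to QTcF has a stated reason: Protocol Section 4.4.5 notes a labelled QT warning. It names no blood pressure signal, and Section 11.1.1.3 lists no events of special interest. All of this stands, and it is why the point is an improvement and not a breach.

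Three stronger readings are tempting, and the documents do not support them.

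- *A reader might infer that no planned table can show a hypertensive child.* Hypertension reported by an investigator would carry a DAIDS grade and appear in the adverse-event tables.
- *A reader might infer that one child's rise would be invisible.* The maximum change is printed by visit and cohort, and every value is in Listing 16.2.8.5. In about 30 children a reader could derive percentiles by hand, although that is not a planned analysis.
- *A reader might infer that averaging repeat readings contradicts the DAIDS lowest-reading rule.* The SAP rule serves summary statistics and the DAIDS rule serves grading. Both can hold, and a graded table need only state which reading it uses.

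The appended table is also not percentile-based throughout, because Grade 1 is a fixed limit. The chance-flag objection to a worst-value table is sound and is answered by reporting the baseline shift and by-visit percentiles with it. The table shells are in a separate document (SAP Section 14.2) that was not available.

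**Conclusion.** The point holds in a limited form. Measured blood pressure is not assessed against the paediatric Grade 2 and 3 limits in any planned table. The raw change that is tabulated mixes growth with any drug effect over up to 2.76 years. Minimum, maximum and listing do not close the gap, because the limit differs by child and changes as the child grows. Systematic detection therefore rests on adverse-event reporting, which omits high readings that lead to no action.

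The size of the missed information cannot be computed from the documents. They give no blood pressure SD, no expected rate of raised pressure and no percentile norms. The 25 mmHg and 10 mmHg values above are illustrative only. The primary PK objective is unaffected. This is a minor but worthwhile change.

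**What to change.** In SAP Section 11.6:

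1. Derive systolic and diastolic percentiles or z-scores for age, sex and most recent height from the norms cited in the DAIDS footnote, and name that reference.
2. Summarise the observed percentile or z-score and its change from baseline by visit, by cohort and overall, next to the raw values.
3. Add one table with number (%) of subjects and shift from baseline to worst post-baseline category: below the 95th percentile; 95th to below the 99th percentile + 5 mmHg; at or above the 99th percentile + 5 mmHg.
4. State that the lowest reading is used when readings are repeated at a visit, for grading only. The mean stays for summary statistics.
5. State that Grade 1 is not used for the count, because its fixed limit lies above the Grade 2 threshold for any child whose 95th percentile is lower.
6. Add a note that a worst-of-11-visits count will flag some children by chance (5% to 43% under the assumptions above), so it is to be read with the baseline shift and the by-visit percentiles.

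The cost is SAP wording, one derivation and one table. No new measurement, visit or procedure is needed.

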12.2.6. Analysis of Effectiveness Variables

Summary statistics will be provided for the number and rate of HAE attacks, duration of symptoms, anatomical location of attacks, use of on-demand rescue medication, number of days with angioedema symptoms, P/C assessment of attack severity, and number of hospitalizations and clinic visits during Part 1 (Weeks 1 through 12) and in Parts 1 and 2 combined (Weeks 1 through 48) by cohort. The rate of HAE attacks over time will be provided. Subjects who discontinue the study due to “lack of efficacy” will be identified and provided in a listing.

12.2.7. Analysis of Exploratory Variables

Summary statistics for the exploratory endpoints related to assessment of palatability and acceptability for the berotralstat granules will be provided for subjects enrolled in Cohorts 2 to 4.

13. STUDY ADMINISTRATION

13.1. Direct Access to Source Data/Documents

13.1.1. Study Monitoring

Before an investigational site can enter a patient into the study, a representative of BioCryst will visit the investigational study site to:

- Determine the adequacy of the facilities
- Discuss with the investigator(s) and other personnel their responsibilities with regards to protocol adherence, and the responsibilities of BioCryst or its representatives. This will be documented in a Clinical Study Agreement between BioCryst and the investigator.

During study conduct, BioCryst or its designee will conduct periodic monitoring visits to ensure that the protocol and Good Clinical Practice (GCP) are being followed. The monitors will review source documents to confirm that the data recorded on eCRFs are accurate. The investigator and institution will allow BioCryst representatives, monitors, or its designees direct access to source documents to perform this verification.

It is important that the investigator(s) and their relevant personnel are available during the monitoring visits and that sufficient time is devoted to the process.

During the study, a monitor from BioCryst or representative will have regular contacts with the investigational site, for the following:

- Provide information and support to the investigator(s).
- Confirm that facilities remain acceptable.
- Confirm that the investigational team is adhering to the protocol, that data are being accurately recorded in the case report forms, and that investigational product accountability checks are being performed.
- Perform source data verification. This includes a comparison of the data in the case report forms with the subject's medical records at the hospital or practice, and other records relevant to the study. This will require direct access to all original records for each subject (eg, clinic charts).
- Record and report any protocol deviations not previously sent to BioCryst.
- Confirm AEs and SAEs have been properly documented on CRFs and confirm any SAEs have been forwarded to BioCryst and those SAEs that met criteria for reporting have been forwarded to the IEC/IRB.

The monitor will be available between visits if the investigator(s) or other staff needs information or advice.

13.1.2. Audits and Inspections

Authorized representatives of BioCryst, US FDA and other regulatory authorities, and/or ethics committees may visit the site to perform audits or inspections, including source data verification.

The purpose of a BioCryst audit or inspection is to systematically and independently examine all study-related activities and documents to determine whether these activities were conducted, and data were recorded, analyzed, and accurately reported according to the protocol, standard operating procedures, ICH/GCP guidelines, and any applicable regulatory requirements. The investigator will permit study-related audits mandated by the sponsor, after reasonable notice, and inspection by domestic or foreign regulatory authorities. The investigator should contact BioCryst immediately if contacted by a regulatory agency about an inspection.

It is important that the investigator and relevant personnel are available during the possible audits or inspections and that sufficient time is devoted to the process.

